#### **9.4. Intraocular Pressure**

IOP scores, changes from baseline and percent change from baseline in pre-injection IOP will be summarized by actual treatment received and analysis visit.

Change after injection in IOP will be summarized repeatedly at 40 ( $\pm 10$ ) and 60 ( $\pm 10$ ) minutes following injection. Subjects with an increase of  $\geq 10$  mmHg at 60 ( $\pm 10$ ) minutes post-injection in IOP will be listed by treatment arm and subject ID. These analyses will be performed for the injection of Lucentis and DE-122, respectively.

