 - If post-injection IOP is > 21 mmHg OR increased ≥ 10 mmHg from pre-injection IOP, IOP measurement will be repeated at 60 (± 10) minutes post-injection.
 - IOP will be measured at 60 (± 10) minutes post-injection, if applicable.
 - If post-injection IOP at 60 (± 10) minutes is ≤ 21 mmHg AND increased < 10 mmHg from pre-injection IOP and there is no concern regarding retinal artery perfusion, DE-122 or Sham IVT will be administered.
 - If post-injection IOP at 60 (± 10) minutes is > 21 mmHg, however the IOP is < 30 mmHg AND increased < 10 mmHg from pre-injection IOP and there is no concern regarding retinal artery perfusion, DE-122 or Sham IVT will be administered per the Clinical Investigator's discretion.
If the Clinical Investigator determine that DE-122 or Sham IVT will Not be administered, the subject will be treated according to the Clinical Investigator's discretion. In addition, the Clinical Investigator has the discretion on whether to have the subject continue or exit the study.
 - **If post-injection IOP at 60 (± 10) minutes is ≥ 30 mmHg OR increased ≥ 10 mmHg from pre-injection IOP, DE-122 or Sham IVT will not be administered.** The subject should be prescribed a topical IOP-lowering medication until he or she returns for follow-up per the Clinical Investigator's discretion (an unscheduled visit may apply), and the event will be reported as

an AE. In addition, the Clinical Investigator has the discretion on whether to have the subject continue or exit the study.

- **Perform DE-122 or Sham administration**, and then perform the following procedures after DE-122 or Sham administration.
- After DE-122 or Sham administration, the following will be performed: (all ophthalmic procedures to be performed OU)
 - Within 30 minutes following DE-122 or Sham IVT
 - Slit-lamp biomicroscopy
 - Indirect ophthalmoscopy
 - IOP measurement 40 (± 10) minutes following DE-122 or Sham IVT injection
 - If post-DE-122 or Sham injection IOP is > 21 mmHg OR increased ≥ 10 mmHg from pre-Lucentis[®] injection, IOP measurement will be repeated at 60 (± 10) minutes post-injection.
 - IOP will be measured at 60 (± 10) minutes following DE-122 or Sham IVT injection, if applicable.

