12.2.6. Intraocular Pressure

IOP will be measured by applanation tonometry and reported in millimeters of mercury (mmHg). On the visit of any IVT injection, IOP will be measured before Lucentis® and 40 (± 10) minutes after Lucentis® injection. If post-injection IOP is > 21 mmHg or increased ≥ 10 mmHg from pre-injection IOP, the IOP will be measured again 60 (± 10) minutes following Lucentis® injection. If there is an increase of ≥ 10 mmHg at 60 (± 10) minutes post-injection, the IOP increase of ≥ 10 mmHg will be reported as an AE.

Moreover, IOP will be measured after DE-122 or Sham injection. If post-DE-122 or Sham injection IOP is > 21 mmHg or increased ≥ 10 mmHg from pre-injection IOP, the IOP will be measured again 60 (± 10) minutes following injection. If there is an increase of ≥ 10 mmHg at 60 (± 10) minutes post-injection compared to pre-injection IOP, the IOP increase of ≥ 10 mmHg will be reported as an AE. This will be also applied for the post IVT injection of Rescue treatment.

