#### 4.3.6. Change after Injection

For any measure assessed pre and post injection, the *change after injection* is defined as:

- Change after injection = post-injection score at the visit – pre-injection score at the visit.

If multiple post-injection scores are available at the visit, then the first observation will be used to derive the change after injection.

If more than one injection were given to the subject at the same visit, change after injection in IOP will be performed for each injection.

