## 6. GENERAL CONSIDERATIONS

Besides data listings, all measures will be summarized by randomized arm and/or overall. Continuous variables will be summarized using descriptive statistics such as number of observations (n), mean, standard deviation, minimum, and maximum. Categorical variables will be tabulated using frequency (n), sometimes along with percentage (%).

All data manipulations and descriptive summaries will be implemented using SAS®, Version 9.4 or later.

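### The 60-minute IOP change in SAP 9.4 covers only eyes already high at 40 minutes, and SAP 4.3.6 keeps that reading out of the variable being summarised

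*SAP*

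**What the plan says.** **Planned summary.** SAP 9.4 (Intraocular Pressure): "Change after injection in IOP will be summarized repeatedly at 40" and 60 minutes, each with a 10-minute window. The same section lists subjects with a rise of 10 mmHg or more at 60 minutes, and applies these analyses to Lucentis and DE-122. Sham is not named.

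**Meaning of a summary.** SAP 6: "Continuous variables will be summarized using descriptive statistics such as number of observations (n), mean, standard deviation, minimum, and maximum", and "all measures will be summarized by randomized arm and/or overall". The opening paragraph of SAP 9.4 classifies by actual treatment received. SAP 6.2 does not impute missing safety values.

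**When the 60-minute reading exists.** Protocol 12.2.6, after Lucentis: "If post-injection IOP is > 21 mmHg or increased ≥ 10 mmHg from pre-injection IOP, the IOP will be measured again 60" minutes after the injection. The second injection has the same condition: "If post-DE-122 or Sham injection IOP is > 21 mmHg or increased ≥ 10 mmHg from pre-injection IOP". The injection-visit sections (for example Protocol 7.5.2.1: "minutes post-injection, if applicable"), Appendix D 23.4.8 and SAP Table 5 also make the reading conditional.

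**Derivation.** SAP 4.3.6: "If multiple post-injection scores are available at the visit, then the first observation will be used to derive the change after injection". Its next sentence has the IOP change derived separately for each injection.

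**The concern.** Two problems meet in one table. First, the 40-minute row rests on all injected eyes and the 60-minute row only on those that met the trigger. A reader who sees the two rows together will take them as a time course, but they describe different eyes. The share of eyes that meets the trigger depends on the IOP effect being assessed, so the selection also differs between arms when the effect does.

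Second, the variable summarised at 60 minutes is defined in a way that leaves the 60-minute reading out. A programmer cannot follow 4.3.6 and 9.4 together.

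Safety is part of the primary objective and the study defines no hypothesis (Protocol 16.2.2), so descriptive tables such as this one are the safety evidence.

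**Working it through.** **1. Do the two SAP rules agree?** IOP is the only measure in SAP Table 5 with a scheduled second reading after the same injection; slit-lamp and ophthalmoscopy have one. The 60-minute reading is taken only after a 40-minute one. For each injection the first observation is therefore the 40-minute value, and a 60-minute value can never enter change after injection. SAP 9.4 asks for that variable at 60 minutes, so the rules conflict.

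**2. Who is in the 60-minute row?** Only eyes with a 40-minute IOP above 21 mmHg or a rise of at least 10 mmHg. The others have no 60-minute value and, without imputation, drop out. The SAP gives no denominator or label for the row.

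**3. Direction of the bias.** Suppose 60-minute change = *f* × 40-minute change + independent noise, where *f* is the persistence. Then

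row mean − all-eyes mean = *f* × (mean 40-minute change in triggered eyes − mean 40-minute change in all eyes).

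If the change is unrelated to the pre-injection level, a larger change makes the trigger more likely. The bracket is then positive, and the bias is upward for any positive *f*.

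**4. Size.** The plan has no IOP figure to reproduce. Every input below is an assumption: pre-injection IOP normal, mean 15, SD 3, limited to 6–21 mmHg; 40-minute change normal with the mean/SD shown; noise SD 1.5. The trigger is the protocol's. Results are simulated, in mmHg.

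| 40-min change, mean/SD | Share re-measured | *f* | 60-min mean, all eyes | 60-min mean, planned row | Excess |
|---|---|---|---|---|---|
| 0 / 2.5 | 5% | 0.4 | 0.0 | 1.5 | 1.5 |
| | | 0.6 | 0.0 | 2.2 | 2.2 |
| | | 0.8 | 0.0 | 3.0 | 3.0 |
| 2 / 3.5 | 18% | 0.4 | 0.8 | 2.4 | 1.6 |
| | | 0.6 | 1.2 | 3.6 | 2.4 |
| | | 0.8 | 1.6 | 4.85 | 3.2 |
| 4 / 4 | 33% | 0.4 | 1.6 | 3.0 | 1.4 |
| | | 0.6 | 2.4 | 4.6 | 2.2 |
| | | 0.8 | 3.2 | 6.1 | 2.9 |

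Excess was computed before rounding. Check of the largest value with the formula in step 3: in the 2 / 3.5 case the triggered eyes average 6.06 at 40 minutes, so the excess is 0.8 × (6.06 − 2.00) = 3.248, about 3.2.

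A wider grid (mean change 0 to 6, SD 3 to 5, *f* of 0.5 or 0.7) gives 6.5% to 50% of eyes re-measured and an excess of about 0.9 to 4.9 mmHg.

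In eyes per visit, 5% of Arm 1 is 0.05 × 17 = 0.85, about one eye. At 33% it is 0.33 × 17 = 5.6 eyes.

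**5. Between arms.** With SD 4 and *f* = 0.7, compare a mean 40-minute change of 0 with one of +4:
- All injected eyes: 60-minute means 0.0 and 2.8, difference 2.8.
- Planned row: 4.07 and 5.33, difference 5.33 − 4.07 = 1.26, resting on about 10% and 34% of eyes.

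In this example the excess is larger in the arm with the smaller true rise (4.07 against 5.33 − 2.8 = 2.53), so a real difference shrinks.

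**The case against.** The best defence is that the intent is clear and little is hidden. SAP 9.4 is the specific provision and names both times, so a sensible programmer would let it override 4.3.6. SAP Table 5 says the second reading is conditional, and SAP 6 prints n, so the smaller count is visible. This stands against any claim that the SAP treats the reading as universal. It does not make the rows comparable: n shows that fewer eyes were measured, not that they were chosen for a high value.

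A reader might infer that 4.3.6 discards the 60-minute reading altogether. It does not. The 9.4 listing can be made from the recorded pre-injection and 60-minute values. A rise of 10 mmHg or more at 60 minutes is also reported as an adverse event (Protocol 12.2.6) and tabulated by actual treatment (SAP 9.1). The key event is therefore not lost.

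The between-arm point also needs limits. SAP 9.4 plans no IOP difference or interval. The Lucentis row compares the same drug and dose in every arm, before that day's DE-122 or Sham. For the second injection, Sham is not named, so a control row is not clearly planned. The distortion in step 5 therefore matters for the two DE-122 doses, and for the control comparison once Sham is included.

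Finally, every simulation input is assumed. That limits what can be said about size.

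**Conclusion.** The point stands, and the SAP should be changed. As written, the plan either contradicts itself (4.3.6 against 9.4) or produces a 60-minute mean over eyes selected for a high 40-minute value. That mean is biased upward relative to all injected eyes and cannot be read against the 40-minute row or across arms. The conflict and the selection follow from the documents alone.

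The upward direction rests on 40- and 60-minute changes being positively related, and on the change not being strongly tied to a low pre-injection level. The size, about 1.4 to 3.2 mmHg with 5% to 33% of eyes re-measured, holds for the main set of assumed IOP values with 40% to 80% persistence, and for nothing wider.

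Two stronger readings are not supported:
- That the table would show IOP still climbing between 40 and 60 minutes. In the 4 / 4 case the row reads 4.6 after 4.0 at 60% persistence, but 3.0 at 40%, so this depends on the value chosen.
- That acute IOP rise is the leading procedural risk here. The documents do not say so; the procedural event they report from the Phase I/II study is subconjunctival haemorrhage.

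The primary efficacy endpoint is not affected.

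**What to change.** - **SAP 9.4, 40 minutes.** Keep the summary of change for every injection given.
- **SAP 9.4, 60 minutes.** Replace the mean with counts by arm and by injection (Lucentis; DE-122 or Sham, with Sham named). The denominator is all injections given. Report (a) repeat reading triggered and (b) rise of at least 10 mmHg at 60 minutes, the event 9.4 already lists. State that an injection with no triggered repeat counts as event not observed.
- **If a 60-minute mean is kept.** Label it *eyes meeting the repeat-measurement trigger only*, and print number measured over number injected.
- **SAP 4.3.6.** State that the first-observation rule does not apply to the 60-minute IOP summary.
- **IOP adverse event criterion.** Protocol 12.2.6 and SAP Table 5 give a rise of at least 10 mmHg; the visit sections and Protocol 23.4.8 give an IOP of at least 30 mmHg or a rise of at least 10 mmHg. These passages must be reconciled. Count (b) is defined by the rise alone and does not depend on which is adopted.

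Cost: SAP wording, one table shell and the reconciliation of the criterion. No new data are needed.

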 - If post-DE-122 or Sham injection IOP at 60 (± 10) minutes is ≥ 30 mmHg OR increased ≥ 10 mmHg from pre-Lucentis[®] injection IOP, the subject should be prescribed a topical IOP-lowering medication, and the IOP elevation will be reported as an AE. Per the Clinical Investigator's discretion, the subject can return for follow-up (an unscheduled visit may apply).
 - If post-DE-122 or Sham injection IOP at 60 (± 10) minutes is > 21 mmHg AND < 30 mmHg, the subject will be treated according to the Clinical Investigator's discretion.
- AE assessments must be performed after each IVT injection.
- Collect blood specimen for the following examinations at 3 hrs (± 10 mins) post DE-122 or Sham injection. If DE-122 or Sham IVT injection is skipped, the blood sampling will be done at 3 hrs (± 10 mins) post Lucentis[®] administration.
 - PK serum sample (**for only the subjects who have consented under the protocol prior to Version 4.0**)
 - Biomarker serum sample
- Upload collected images (SD-OCT) of the study eye to the central reading center.
- Schedule the subject to return for Visit 2 (Day 3) or Visit 3 (Week 1 (D8 \pm 1)).

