23.4.8. Intraocular Pressure

IOP will be measured by applanation tonometry at each study visit except Visit 2 (Day 3), Visit 9 (Week 20 + 2 days) and Visit 10 (Week 20 + 7 days).

At visits with IVT injection, IOP will be measured before Lucentis® injection and 40 (± 10) minutes after injection. If post-Lucentis® injection IOP is > 21 mmHg or increased ≥ 10 mmHg from pre-injection IOP, the IOP measurement will be repeated at 60 (± 10) minutes following Lucentis® injection.

If post-injection IOP at 60 (± 10) minutes is ≥ 30 mmHg OR increased ≥ 10 mmHg from pre-injection IOP, the subject should be prescribed a topical IOP-lowering medication until he or she returns for follow-up per the Clinical Investigator's discretion, and the event will be reported as an AE.

IOP will be also measured after DE-122 or Sham injection. If post-DE-122 or Sham injection IOP is > 21 mmHg OR increased ≥ 10 mmHg from pre-Lucentis® injection at 40 (± 10) minutes after injection, the IOP measurement will be repeated at 60 (± 10) minutes after the injection. If post-DE-122 or Sham injection IOP at 60 (± 10) minutes is ≥ 30 mmHg OR increased

≥ 10 mmHg from pre-Lucentis® injection IOP, the subject should be prescribed a topical IOP-lowering medication, and the IOP elevation will be reported as an AE. If post-injection IOP at 60 (± 10) minutes is > 21 mmHg AND < 30 mmHg, the subject will be managed according to the Clinical Investigator's discretion.

If rescue IVT injection is performed, IOP will be measured 40 (± 10) minutes after the injection. If post-injection IOP is > 21 mmHg OR increased ≥ 10 mmHg from pre-injection IOP, IOP measurement will be repeated at 60 (± 10) minutes post-injection. If post-injection IOP at 60 (± 10) minutes is ≥ 30 mmHg OR increased ≥ 10 mmHg from pre-injection IOP, the subject should be prescribed a topical IOP-lowering medication, and the IOP elevation will be reported as an AE. Per the Clinical Investigator's discretion, the subject can return for follow-up. If post-injection IOP at 60 (± 10) minutes is > 21 mmHg AND < 30 mmHg, the subject will be managed according to the Clinical Investigator's discretion.

The applanation tonometer must be calibrated for accuracy before the first subject undergoes screening, and periodically until the last subject has exited the study. For checking calibration, follow the manufacturer's instructions.

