**Table 5: Safety Measures**

Safety Measure	Note
Intraocular pressure (IOP)	
IOP will be measured by applanation tonometry and reported in millimeters of mercury (mmHg). The IOP of an eye is derived as the mean/median of two or three consecutive IOP measurements.
 
IOP will be measured before Lucentis® and 40 (±10) minutes after Lucentis® injection. If applicable, IOP will be measured again 60 (±10) minutes following Lucentis® injection. Any increase of ≥ 10 mmHg in IOP at 60 (±10) minutes post-injection will be reported as an AE.
 
The procedure will be also applied for DE-122 or Sham injection, and any post IVT injection of rescue treatment.

Slit-lamp biomicroscopy findings: lid Redness lid edema conjunctival hyperemia conjunctival edema corneal edema anterior chamber cells anterior chamber flare iris pupil lens phakic lens severity	
Slit-lamp biomicroscopy will be performed prior to Lucentis® injection and within 30 minutes after DE-122 or Sham injection, and any post IVT injection of rescue treatment.
 
Anterior Chamber Cells will be graded as 0 = No cells, 0.5 = 1-5 cells, 1 = 6-15 cells, 2 = 16-25 cells, 3 = 26-50 cells, or 4 = >50 cells.
 
Anterior Chamber Flare will be graded as 0 = None, 1 = Faint, 2 = Moderate, 3 = Marked, or 4 = Intense.
 
The iris and pupil status of an eye will be graded as either normal or abnormal.
 
The lens of an eye will be classified as phakic, aphakic, or pseudophakic.
 
The rest biomicroscopy parameters will be graded as 0 = None, 1 = Mild, 2 = Moderate, or 3 = Severe.

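### SAP 9.4 does not name Sham in the post-injection IOP analysis, and its listing omits the protocol's 30 mmHg criterion

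*SAP*

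**What the plan says.** **Scope of the analysis.** SAP 9.4 plans a summary of the change in IOP after injection at 40 and 60 minutes, and a listing by arm of subjects whose IOP is up by at least 10 mmHg at 60 minutes. It closes with: "These analyses will be performed for the injection of Lucentis and DE-122, respectively". SAP Table 5 describes the readings around the Lucentis injection and then says: "The procedure will be also applied for DE-122 or Sham injection, and any post IVT injection of rescue treatment". SAP 4.3.6 says that, where a visit has more than one injection, "change after injection in IOP will be performed for each injection".

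**Reference value.** SAP 4.3.6 subtracts the "pre-injection score at the visit" and does not say which reading that is for the second injection. It also says that, where there are several post-injection readings, the first is used.

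**Threshold.**
- SAP Table 5: "Any increase of ≥ 10 mmHg in IOP at 60 (±10) minutes post-injection will be reported as an AE".
- Protocol 12.2.6, second injection, at 60 "minutes post-injection compared to pre-injection IOP, the IOP increase of ≥ 10 mmHg will be reported as an AE".
- Protocol 7.5.2.1 has a wider condition: "If post-DE-122 or Sham injection IOP at 60 (± 10) minutes is ≥ 30 mmHg OR increased ≥ 10 mmHg from pre-Lucentis" injection IOP. The subject then gets pressure-lowering drops and the elevation is reported as an AE.
- Protocol 23.4.8 repeats it: "If post-DE-122 or Sham injection IOP at 60 (± 10) minutes is ≥ 30 mmHg OR increased" by 10 mmHg or more from the pre-Lucentis value.

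**The concern.** The primary objective includes safety of the combination against Lucentis alone. A second intravitreal injection on the same day adds volume to the eye, so the short-term pressure response is a direct safety question for this regimen. Arm 1 has a sham that does not enter the eye and is followed by the same pressure checks. Its post-Sham readings show what happens at that point of the visit without the added volume. If the post-DE-122 change is tabulated with nothing beside it, the reader cannot separate the effect of the second injection from the tail of the Lucentis injection.

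The threshold matters for a different reason. The dedicated IOP listing should contain the events that the protocol itself treats as pressure events. With only the relative rise, it leaves out eyes that reach 30 mmHg from a high starting value.

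**Working it through.** The plan gives no figure to reproduce. The check sets the rules side by side and works out which eyes fall between them.

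**1. What is lost if Sham is left out**

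Inputs: volumes from the Protocol synopsis and 7.3; arm sizes 17, 31 and 28 from SAP 3.3; six planned injections from SAP 3.1.

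- Volume into the eye per visit: Arm 1, 50 µL; Arm 2, 50 + 20 = 70 µL; Arm 3, 50 + 40 = 90 µL.
- Planned second procedures: Sham 17 × 6 = 102; DE-122 (31 + 28) × 6 = 59 × 6 = 354.
- Timing: the first post-Lucentis check is nominally at 40 minutes, and the first check after the second procedure comes 40 minutes after that procedure. The second check is therefore nominally at least 40 + 40 = 80 minutes after Lucentis. Arm 1's post-Lucentis reading, which 9.4 does keep, is at a different point of the visit. Only the post-Sham reading matches.

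**2. Which eyes meet the protocol rule but miss the listing**

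Let p be the pre-Lucentis IOP and r the 60-minute reading.

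- Protocol 7.5.2 and 23.4.8 report if r ≥ 30 or r − p ≥ 10.
- SAP 9.4 lists if r − p ≥ 10, taking p as the reference.
- The gap is r ≥ 30 with r − p < 10. Then p > r − 10 ≥ 20, so only eyes starting above 20 mmHg can fall into it.

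Recorded IOP can fall on half units, because it may be the mean of two readings (Protocol 23.4.8). In 0.5 mmHg steps:

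| p | r reported but not listed | Largest unlisted rise |
|---|---|---|
| 20 | none (30 − 20 = 10, listed) | – |
| 20.5 | 30 | 30 − 20.5 = 9.5 |
| 21 | 30 to 30.5 | 30.5 − 21 = 9.5 |
| 22 | 30 to 31.5 | 31.5 − 22 = 9.5 |
| 25 | 30 to 34.5 | 34.5 − 25 = 9.5 |

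If pre-Lucentis IOP never exceeds 21 mmHg, only the 20.5 and 21 rows apply. That is an assumption: exclusion criterion 2 uses 21 mmHg as its limit for uncontrolled glaucoma, but it governs entry, not later visits.

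**3. Which reference the documents point to**

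SAP Table 5 describes one reading before injection, taken before Lucentis. Footnote c of SAP Table 1 has IOP before and after Lucentis and then again after DE-122 or Sham, with no separate reading labelled as preceding the second procedure. Protocol 7.5.2 and 23.4.8 name the pre-Lucentis value for the second injection. The better-supported reading is therefore pre-Lucentis; SAP 4.3.6 just does not say so.

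**4. First observation against two time points**

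The first-observation rule in 4.3.6 would keep the 40-minute value whenever both exist. SAP 9.4 asks for both 40 and 60 minutes. Applied as written, the 4.3.6 rule would leave no derived 60-minute change for those eyes.

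**The case against.** **Sham may simply be shorthand.** SAP 4.3.6 takes the change for each injection, Protocol 10.7 calls Sham an injection, the 9.4 listing is by arm, and SAP 9 classifies all safety summaries by actual treatment. The documents abbreviate in the same way elsewhere: SAP 7.7 speaks only of skipped DE-122, and Protocol 23.4.7 only of DE-122 visits for the slit-lamp check. This stands. The lost control column is what the sentence says literally; it is not shown to be the intention.

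**Sites will report 30 mmHg anyway.** A reader might infer that such events go unreported because of 12.2.6. The documents do not support that. Protocol 7.5 sends sites to 23.4 for procedures, 23.4.8 has both limbs, and so do the instructions at each injection visit. Section 12.2.6 is narrower but does not forbid reporting. What remains is an inconsistency within the protocol and a listing that follows its narrower section.

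**The reference could hide large rises.** A reader might infer that the second-injection change is taken stepwise. For 12 → 21 → 30 mmHg, the second injection is allowed at 21 (21 − 12 = 9). The stepwise change is then 30 − 21 = 9, unlisted, although the day's rise is 30 − 12 = 18. In 0.5 mmHg steps, total rises of 10 to 19 could escape the listing this way. The documents do not support this as the plan's effect. They point to the pre-Lucentis reference, under which every such eye is listed, and each is a reportable AE under 7.5.2 on either reading.

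**The trial is descriptive.** True, and no error rate is involved. But safety is part of the primary objective, and these descriptive outputs are the evidence for it.

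**Conclusion.** Two drafting faults hold. As worded, SAP 9.4 leaves the post-Sham readings out of the second-injection IOP analysis, probably as shorthand. The 9.4 listing, SAP Table 5 and Protocol 12.2.6 lack the 30 mmHg limb that Protocol 7.5.2 and 23.4.8 apply. A silent reference and a conflicting first-observation rule in SAP 4.3.6 should be tidied at the same time.

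The size is modest. Up to 102 planned sham procedures are at issue, if all six are given to all 17 subjects. The threshold gap reaches only eyes starting above 20 mmHg, taking pre-Lucentis IOP as reference, and the documents give no basis for counting them. Events reported under 7.5.2 appear in the AE tables by arm, and raw values are listed under Protocol 16.2. The Stage 1 pressure criterion in Protocol 7.4.1 excludes the injection day, so dose decisions there are not affected. The primary endpoint is not affected. This is worth correcting before the tables are programmed, but it is not a threat to the trial's conclusions.

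**What to change.** - **SAP 9.4, scope:** name Lucentis, and DE-122 or Sham, as the injections analysed, and present the results by arm.
- **SAP 9.4 listing and SAP Table 5:** at 60 minutes, use 30 mmHg or more, or a rise of 10 mmHg or more from pre-Lucentis IOP.
- **SAP 4.3.6:** state that the second-injection change is taken from pre-Lucentis IOP, as the protocol already does, and that the first-observation rule does not override the separate 40- and 60-minute summaries in 9.4.
- **Protocol 12.2.6:** align with 7.5.2 and 23.4.8 at the next amendment, or by a clarification. SAP 3.1 describes the 76 subjects as already randomised, so this alone would not justify an amendment.

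The cost is a few lines of SAP text, Sham results in one safety table and possibly a few more rows in one listing. All the readings are already collected.
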